1. Safety Evaluations: Will assess for the safety of anti-SARS-CoV-2 plasma in terms of treatment emergent adverse events.
2. Clinical evaluations: Vital signs and symptom screen on days 0-28 (or until hospital discharge, whichever is sooner).
3. Laboratory evaluations:
4. Safety laboratory tests (ABO typing, pregnancy testing, CBC and comprehensive metabolic panel) will be performed at the local CLIA-certified hospital clinical laboratory on days 0-14 (or until hospital discharge, whichever is sooner).

Adverse event reporting

An Adverse Event (AE) is any untoward or unfavorable medical occurrence in a human subject administered an investigational product, including any abnormal sign, symptom or disease, temporally associated with the subject's participation in research, whether or not considered related to the subject's participation in the research.

An AE does not include the following:

- Medical or surgical procedures such as surgery, endoscopy, tooth extraction, and transfusion. The condition that led to the procedure may be an AE and must be reported.
- Preexisting diseases, conditions, or laboratory abnormalities present or detected before the screening visit that do not worsen
- Situations where an untoward medical occurrence has not occurred (e.g., hospitalization for elective surgery, social and/or convenience admissions)
- Any medical condition or clinically significant laboratory abnormality with an onset date before the investigational product is administered to the subject and not related to a protocol-associated procedure is not an AE. It is considered to be preexisting and should be documented as medical history.

Preexisting events or conditions that increase in severity or change in nature after the subject receives the investigational product will be considered AEs.

Serious Adverse Event (SAE): any adverse event temporarily associated with the subject's participation in research that meets any of the following criteria:

- Results in death;
- Is life-threatening (places the subject at immediate risk of death from the event as it occurred);
- Requires inpatient hospitalization or prolongation of existing hospitalization;
- Results in a persistent or significant disability/incapacity;
- Results in a congenital anomaly/birth defect; or

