Follow-up information to a safety report will be submitted as soon as the relevant information is available. However, if the results of a sponsor's investigation show that an adverse drug experience not initially determined to be reportable are so reportable, the sponsor must report such experience as soon as possible, but no later than 15 calendar days after the determination is made.

SAFETY OVERSIGHT

Monitoring Plan

1. All AEs and SAEs will be reviewed by the study team in real time.
2. A data safety monitoring board (DSMB), composed of independent experts without conflict of interests will be established. The Board will review the study before initiation and quarterly thereafter.

The Board will review study data to evaluate the safety, efficacy, study progress, and conduct of the study.

Study monitoring

As per ICH-GCP 5.18 and FDA 21 CFR 312.50, clinical protocols are required to be adequately monitored by the study sponsor. Monitors will verify that

- (1) There is documentation of the informed consent process and signed informed consent documents for each subject
- (2) There is compliance with recording requirements for data points
- (3) All SAEs are reported as required
- (4) Individual subjects' study records and source documents align
- (5) Investigators are in compliance with the protocol
- (6) Regulatory requirements as per Office for Human Research Protections (OHRP), FDA, and applicable guidelines (ICH-GCP) are being followed.

Halting Criteria for the Study

The study enrollment and dosing will be stopped and an ad hoc review will be performed if any of the specific following events occur or, if in the judgment of the study physician, subject safety is at risk of being compromised:

- 1. Unexpected death of a dosed subject in relation to infusion
- 2. Occurrence of a life-threatening allergic/hypersensitivity reaction (anaphylaxis), manifested by bronchospasm with or without urticaria or angioedema requiring hemodynamic support with pressor medications or mechanical ventilation.
- 3. One subject with an unexpected SAE associated with study product.
- 4. Two subjects with a Grade 3 or higher toxicity for the same parameter associated with study product.
- 5. An overall pattern of symptomatic, clinical, or laboratory events that the medical monitor, ISM, or SMC consider associated with study product and that may appear minor in terms of individual events but that collectively may represent a serious potential concern for safety.

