- 6. Any other event(s) which is considered to be a serious adverse event in the good clinical judgment of the responsible physician. This will be appropriately documented.

Furthermore, given that ADE may be an issue with convalescent antibody treatment, out of an abundance of caution we will monitor the number of subjects in each trial arm that progresses to an indication for need of mechanical ventilation. In monitoring the number of subjects that progresses to this stage, we will present these data to the DSMB and a masked outcomes assessor so that they may objectively evaluate and determine whether they would like to be unmasked. After at least 50% of trial participants have accumulated follow-up, the number of subjects that progress to this stage will be presented to the masked outcomes assessor and formally asked whether they (1) see a clinically meaningful difference between trial arms and (2) if so do they require a formal interim analysis. At any point should the DSMB require a formal interim analysis, we will examine the difference in treatment arms for need for mechanical ventilation. This interim analysis will adjust for factors related to need for mechanical ventilation including age and presence of cardiopulmonary comorbidities.

Upon completion of this review and receipt of the advice of the DSMB, the IND sponsor will determine if study entry or study dosing should be interrupted or if study entry and study dosing may continue according to the protocol. Should the trial not be stopped at this time point, the final analysis would

need to account the number of interim analyses that were conducted. Therefore, we would penalize any final analysis dividing our 0.05 alpha in half for each interim analysis.

REFERENCES

- Arabi, Y. M., Hajeer, A. H., Luke, T., Raviprakash, K., Balkhy, H., Johani, S., . . . Alahmadi, M. (2016). Feasibility of Using Convalescent Plasma Immunotherapy for MERS-CoV Infection, Saudi Arabia. *Emerg Infect Dis*, 22(9), 1554-1561. doi:10.3201/eid2209.151164
- Austin, P. C., & Fine, J. P. (2017). Practical recommendations for reporting Fine-Gray model analyses for competing risk data. *Stat Med*, 36(27), 4391-4400. doi:10.1002/sim.7501
- Casadevall, A., & Pirofski, L. A. (2003). Antibody-mediated regulation of cellular immunity and the inflammatory response. *Trends Immunol*, 24(9), 474-478. doi:10.1016/s1471-4906(03)00228-x

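### Halting item 6 is not tied to the study plasma, so read literally a COVID-19 death after infusion stops enrollment and dosing

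*Combined protocol and SAP*

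**What the plan says.** All references are to the combined protocol and SAP.

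The lead sentence of Halting Criteria for the Study is mandatory: "The study enrollment and dosing will be stopped and an ad hoc review will be performed if any of the specific following events occur". It also has a discretionary trigger, "if in the judgment of the study physician, subject safety is at risk of being compromised". Six items follow:

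- Item 1: "Unexpected death of a dosed subject in relation to infusion".
- Item 2: a life-threatening anaphylactic reaction, described specifically.
- Item 3: "One subject with an unexpected SAE associated with study product".
- Item 4: the same Grade 3 or higher toxicity in two subjects, linked to the product.
- Item 5: a pattern of events considered linked to the product.
- Item 6: "Any other event(s) which is considered to be a serious adverse event in the good clinical judgment of the responsible physician".

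Adverse event reporting defines an adverse event as "any untoward or unfavorable medical occurrence in a human subject administered an investigational product", and counts it "whether or not considered related to" taking part in the research. A preexisting condition that worsens after the product is given is an adverse event. An adverse event that results in death is serious. Neither this section nor the halting section exempts progression of COVID-19.

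Secondary and Ancillary Analyses assumes 20% mortality to day 28 and 43 events in 220 participants. Separately, the halting section monitors progression to mechanical ventilation by arm, with a formal question to a masked assessor once at least half of the participants have follow-up.

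**The concern.** The judgment that item 6 asks of the physician is whether an event is serious, not whether plasma may have caused it. In a population with severe COVID-19, serious events and deaths from the disease itself are expected. Followed to the letter, item 6 applies the same mandatory stop to those events as to a reaction to plasma, so the rule cannot separate a product signal from background mortality.

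What is at stake is trial conduct. Staff must either pause for expected deaths or depart from the written rule, while Study monitoring has monitors check compliance with the protocol. If item 6 is meant more narrowly, the text does not say which serious events stop the study.

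**Working it through.** **Step 1: the text.**

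1. The lead sentence makes the stop and review automatic once any listed event occurs.
2. COVID-19 is present at enrollment. Its worsening after the product counts as an adverse event under the preexisting-condition rule, and relatedness is not required.
3. If the worsening results in death, the event is serious by definition.
4. A COVID-19 death unrelated to the plasma falls outside items 1 to 5, so it is an other serious event and meets item 6.

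**Step 2: consistency with the rest of the plan.**

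- Item 1 limits deaths to unexpected ones related to infusion. Literal item 6 catches the remaining post-product deaths, so that limit has no effect.
- Item 3 limits serious events to unexpected ones linked to product. Literal item 6 removes both limits.
- Item 4 waits for a second subject. If the toxicity is serious, literal item 6 stops the study at the first.
- The by-arm ventilation monitoring lets cases accumulate and poses its formal question at 50% follow-up. That fits poorly with a rule under which each serious progression has already stopped the study.

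**Step 3: size, counting deaths only.** Inputs: mortality 20% and N = 220 (Secondary and Ancillary Analyses); 219 participants split 146 and 73 (Primary Analysis, go/no-go decision, and power consideration). Expected deaths = N × p; chance of at least one death in n participants = 1 − (1 − p)^n.

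The plan's own figure: 0.20 × 219 = 43.8 and 0.20 × 220 = 44.0, against 43 stated. It is reproduced to within about one death.

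*Both arms in scope:*

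- Expected deaths: about 44 in 220.
- At least one death in 5 participants: 1 − 0.8^5 = 0.672.
- At least one death in 10 participants: 1 − 0.8^10 = 0.893.

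*Strict scope.* Intervention names only convalescent plasma as the investigational product, and the adverse event definition requires that product. Assuming the same mortality in both arms:

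- Expected deaths: 0.20 × 146 = 29.2.
- Chance per randomized participant of an in-scope death: 0.20 × 2/3 = 0.1333.
- At least one in 5 randomized: 1 − 0.8667^5 = 0.511.
- At least one in 10 randomized: 1 − 0.8667^10 = 0.761.

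*Assumed mortality range of 10% to 30%:* 22 to 66 deaths in 220, or 14.6 to 43.8 in 146.

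These are expected deaths, not pauses. A death before infusion is outside the definition, and a death during an existing pause adds no new one. Non-fatal serious events are left out because no rate is given.

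**The case against.** The strongest reply is that item 6 closes a list whose other items concern infusion, product or one specific reaction, and should be read in that light. A reading that empties items 1 and 3 is a reason to doubt the reading. A death needs no clinical judgment to be serious, so the appeal to judgment suggests discretion. The planned 43 deaths, the ventilation monitoring and the 48-hour reporting of serious events to the DSMB all indicate that disease progression was to be followed by other routes. A broad trigger followed by review is also a defensible cautious choice where antibody-mediated enhancement is a concern.

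Much of this stands: the intent was probably narrower than the text. It does not cure the wording. Item 6 does not mention product, the lead sentence already supplies a discretionary clause, and item 5 already covers product-linked patterns.

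A reader might infer three stronger things that the documents do not support:

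- **That the trial would be halted some 43 times, with a calculable delay.** Deaths are not pauses, and neither accrual rate nor review time is given.
- **That no restart route exists.** The sentence giving the sponsor the decision on study entry and dosing follows the ventilation paragraph, but it closely tracks the lead sentence and can be read as covering any halt review.
- **That COVID-19 deaths should be exempted outright.** Enhancement by antibody could look like disease progression, so a blanket exemption could hide the very risk the plan monitors.

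**Conclusion.** Wrong as written, minor severity. The conclusion rests on the literal text of item 6 together with the lead sentence and the adverse event definitions. It does not claim that the authors intended this result or that sites applied it; the documents do not show how the rule was used.

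The consequence is a pause with review, not termination. Its potential scope is about 44 expected deaths if both arms count and about 29 on the strict definition of investigational product. Both figures rest on the plan's 20% mortality, and the second also on equal mortality across arms.

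**What to change.** Replace item 6 with:

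> Any other serious adverse event, expected or unexpected, for which the responsible physician judges there is a reasonable possibility that it was caused by the study plasma (either arm), including serious TRALI or TACO. This will be appropriately documented.

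The causality standard is the one already used for suspected adverse reactions in Adverse event reporting. The words on either arm settle the scope question. The item stays deliberately broader than item 3, and it can still act before item 4 reaches two subjects when a plausibly caused toxicity is serious.

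Add no blanket exemption for death or ventilation. Events judged unrelated continue through the 48-hour reporting to the DSMB and the by-arm ventilation monitoring. Leave the lead sentence and items 1 to 5 unchanged.

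The cost is one reworded item in a protocol amendment. The investigator's report already includes relatedness to the investigational product; for control recipients it should be read as covering control plasma. Sample size and analysis do not change.

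The downside is that relatedness would be judged by a clinical team that Intervention says is not blinded. A TRALI, TACO or enhancement event could be put down to COVID-19. The discretionary clause in the lead sentence, item 5 and DSMB review limit that risk but do not remove it.

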Exclusion Criteria for Enrollment 1. Participation in another clinical trial of anti-viral agent(s)* for COVID-19 2. Receipt of any anti-viral agent(s)* with possible activity against SARS-CoV-2 < 24 hours prior to plasma infusion. 3. Mechanically ventilated (including VV-ECMO) ≥ 5 days 4. Severe multi-organ failure 5. History of allergic reactions to transfusion blood products per NHSN/CDC criteria 6. Known IgA deficiency 7. Females who are pregnant or breastfeeding. *Use of remdesivir as treatment for COVID-19 is permitted.

Subject Withdrawal

Subjects can terminate study participation and/or withdraw consent at any time without prejudice. II. Randomized subjects who withdraw from the study will not be replaced. III. The investigator may withdraw subjects if they are lost to follow up, non-compliant with study procedures or if the investigator determines that continued participation in the study would be harmful to the subject or the integrity of the study data. IV. Discontinuation of the study: The study sponsor, FDA and IRB all have the right to terminate this study at any time.

Intervention

Subjects will be randomized in a 2:1 ratio, stratified by country, to receive treatment vs. frozen fresh plasma. II. Study drug: The investigational product is anti-SARS-CoV-2 plasma. Patients identified as having recovered from COVID-19 will serve as potential donors. Testing will confirm presence of anti-SARS-CoV-2 antibody prior to donation. Potential donors and samples will be screened for transfusion-transmitted infections (e.g. HIV, HBV, HCV, WNV, HTLV-I/II, T. cruzi, ZIKV) and plasma will be collected using apheresis technology. This is similar to standard blood bank protocols. III. Active arm will receive 1 unit of anti-SARS-CoV-2 plasma. IV. Control arm will receive 1 unit of control plasma. V. The study drug will be in a standard plasma unit bag, with a studyspecific ISBT label and will include the following statement: "Caution: New Drug--Limited by Federal (or United States) law to investigational use." VI. The blood bank will not be blinded to treatment allocation, nor will the clinical study team. VII. The patient and the clinician who will assess the end of treatment outcome will be blinded to treatment allocation.

Randomization

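### The mid-trial ventilation look gives by-arm counts, and an option to be unmasked, to a masked outcomes assessor who may be the Day 28 rater

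*Combined protocol and SAP*

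**What the plan says.** Two parts of the protocol bear on this.

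**Who is blinded.** Under Intervention: "The patient and the clinician who will assess the end of treatment outcome will be blinded to treatment allocation". The item before it reads: "The blood bank will not be blinded to treatment allocation, nor will the clinical study team". The Study Design paragraph of the synopsis agrees: the patient and the clinician assessing outcome are the blinded parties.

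**Who sees accumulating data.** Under Safety Oversight, Halting Criteria for the Study: "we will monitor the number of subjects in each trial arm that progresses to an indication for need of mechanical ventilation". Of the recipients it says "we will present these data to the DSMB and a masked outcomes assessor so that they may objectively evaluate". The choice about masking is left to these same recipients, who are to "determine whether they would like to be unmasked". A further look comes once at least half of the participants have follow-up, when "the number of subjects that progress to this stage will be presented to the masked outcomes assessor". That person is formally asked whether they "see a clinically meaningful difference between trial arms" and, if so, whether a formal interim analysis is needed.

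The primary endpoint is the Day 28 score on the seven-category scale. Invasive ventilation falls in category 6. Categories 1 and 2 differ only in whether a discharged patient has resumed normal activities, and no operational definition is given.

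**The concern.** Apart from the patient, the only person whose blinding protects the Day 28 score is the clinician who rates it. The safety rule hands comparative data to someone described as a masked assessor of outcomes, asks for a judgement on whether the arms differ, and offers unmasking. The question cannot be answered without data split by arm.

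The rule states no safeguard. It does not require coded labels, a separate person for the safety look, replacement of an assessor who has been unmasked, or restriction of by-arm data to the DSMB.

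If this person also rates Day 28, up to about half of the primary outcomes would be scored after the 50% look by someone who has seen the trend and may know the allocations. The credibility of the go decision would suffer, mainly where the scale calls for judgement.

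**Working it through.** There is no figure in the plan to reproduce. The check has a reading step and three calculations.

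**1. Is the assessor the Day 28 rater?** The blinding statements name a clinician who assesses outcome. The halting section speaks of a masked outcomes assessor. No sentence equates them, and no sentence describes a second masked assessor. Identity is the natural reading but is not stated.

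**2. What do the arm sizes reveal?** With N = 220 and 2:1 allocation, the 50% look covers 110 participants: 110 × 2/3 = 73.3 on plasma and 110 × 1/3 = 36.7 on control, about 73 vs 37. Denominators would identify the plasma column even under coded labels. If only counts were shown and ventilation risk were equal, take X ~ Bin(73, r) and Y ~ Bin(37, r). P(X > Y) is then about 0.84, 0.95 and 0.98 for assumed r of 10%, 20% and 30%. This identifies a column, not any patient.

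**3. What could differential scoring do?** This is conditional on patient-level unmasking at the 50% look.

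- From the protocol: 146 vs 73, a one-sided Mann-Whitney test, and the levels 15% and .015. The Statistical Analysis section uses both levels, so both are shown.
- Assumed: no true effect, and Day 28 categories 1 to 7 at 22/30/5/8/5/10/20%. The documents give no distribution; the last figure matches their 20% mortality assumption. The test is unstratified.
- Statistic: Z = (U − n₁n₂/2) / √{(n₁n₂/12)[(N+1) − Σ(t³ − t)/(N(N − 1))]}. Here n₁ = 146, n₂ = 73, N = 219, and t is the number of patients tied in each category. The one-sided p is Φ(Z), since low scores are good.
- Plasma patients scored after the look: 146 − 73 = 73, of whom 73 × 0.30 = 21.9 are expected in category 2.

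| Later plasma patients rescored | Expected number | False-go at 15% | False-go at .015 |
|---|---|---|---|
| None | 0 | 15% | 1.5% |
| 10% of category 2, to 1 | 21.9 × 0.10 = 2.2 | 17.4% | 1.8% |
| 15% of category 2, to 1 | 21.9 × 0.15 = 3.3 | 18.7% | 2.1% |
| 25% of category 2, to 1 | 21.9 × 0.25 = 5.5 | about 21% | about 2.5% |
| 10% of category 1, to 2 | 73 × 0.22 × 0.10 = 1.6 | about 13.5% | lower than 1.5% |

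Rates are simulated, and repeat runs differ by a few tenths of a point. Two other assumed distributions with 20% mortality (25/25/5/8/7/10/20 and 45/20/3/4/3/5/20) give 16% to 17% for a 10% shift and 20% to 21% for a 25% shift at the 15% level.

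**4. Does knowing the trend alone do this?** When the same 15% upgrading is applied to both arms, the rates stay at 15.0% and 1.5%. Inflation needs scoring that differs by arm, and so needs individual allocation.

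**The case against.** The strongest reply is that the rule does not break any blind as written.

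- The assessor in the halting section may be someone other than the Day 28 rater. This stands as an uncertainty, and it is why confidence is medium.
- Unmasking is optional, and its scope is not stated. In a sentence about aggregate counts it may mean only decoding the arm labels. This stands too.
- Most of the scale is hard to misrate. Categories 3 to 7 are defined by hospitalization, level of support or death, and the patient is also blinded. That confines the exposure largely to category 1 versus 2.
- The look exists because harm from plasma is feared, so an assessor might score plasma worse. The last row of the table shows the false-go rate then falls, so the direction of any bias is not known.

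Three stronger readings are tempting. A reader might infer that the rule in itself breaks the blind; that would need both the identity of the assessor and patient-level unmasking, and the text states neither. A reader might infer that 2:1 arm sizes give the allocation away; they can identify the plasma column but no patient. A reader might also apply a 10% misrating to all 146 plasma patients (146 × 0.30 × 0.10 = 4.4) and obtain about 19.8% at the 15% level; patients already scored before the look cannot be affected by it.

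What remains is that the text routes by-arm data and an unmasking option to a person it calls a masked assessor of outcomes, with nothing to keep that person away from the primary endpoint.

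**Conclusion.** The point holds as a route to breaking the blind, not as a demonstrated break. The blinding statements and the monitoring rule need to be reconciled.

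The size is modest and conditional. With patient-level unmasking and favourable misrating of 10% to 25% of later plasma patients in category 2, the false-go rate is about 17% to 21% against 15%, or about 1.8% to 2.5% against 1.5%. With unfavourable misrating of 10% of those in category 1, it is about 13.5% against 15%. Without individual allocation there is no such effect.

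These figures rest on an assumed Day 28 distribution, no true effect, an unstratified test, and half of the plasma arm being scored after the look. The protocol says at least half must have follow-up, so the formal look could come later and touch fewer patients. The figures are illustrations, not predictions. Confidence is medium because the assessor's identity is inferred.

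**What to change.** In Halting Criteria for the Study, remove the outcomes assessor from the recipients of the ventilation counts and put the 50% question to the DSMB alone. The DSMB already receives these data, reviews safety and efficacy under the Monitoring Plan, and can require the formal interim analysis, so surveillance for enhancement loses nothing.

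Add one sentence stating that no one who scores the Day 28 scale sees by-arm data or is unmasked before database lock.

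If the sponsor intends a separate person for the safety look, the protocol should say so; that same sentence would then be sufficient.

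The cost is protocol wording only, with no change to sample size, visits or analysis.

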- Levels of SARS-CoV-2 RNA on Days 0, 7, and 14.
- Duration of need for supplemental oxygen and/or mechanical ventilation
- Duration of hospitalization
- Mortality.

Statistical Analysis

• Efficacy Objective

1. Primary Analysis, go/no-go decision, and power consideration

The primary analysis of the endpoint will be a one-sided nonparametric stratified Mann-Whitney test; stratification is done by country (US, Brazil). A “go decision” in this phase 2 trial will be a one-sided $P < .015$, suggesting evidence of promise of the treatment arm for further investigation in a phase 3 trial. Adaptive seamless phase 2/3: The results in this proof-of-concept study will be used to plan the sample size in a Phase 3 trial, which may include the data in this Phase 2 in the final analysis using adjusted P value as in a seamless phase 2/3 trial. Details of P value adjustment and sample size calculation will be decided before the final analysis of this study data.

The calculation was based on blinded pooled data of the Day 28 outcome and an odds ratio of 1.7 under a proportional odds assumption. With a 2:1 randomization ratio and a total sample size of 219 participants (146 in convalescent plasma vs. 73 control), a onesided Mann Whitney test at 15% level will have about 82% power to detect an odds ratio of 1.7. Since the difference in power between 219 and 220 is minimal, $N=219$ can be used to justify an enrollment total of 220. We note a recent study of antiviral drug yields an odds ratio of 1.15, with 95% CI: 0.67 to 1.96, which covers our assumed odds ratio.

2. Secondary and Ancillary Analyses

All secondary and ancillary efficacy analyses will also be intent-to-treat. With a sample size of 220, assuming 20% mortality up to day 28, we expect a total of 43 events. Longitudinal data collected over multiple days during the study period (e.g., PCR positivity, RNA) will be analyzed using the framework of generalized linear mixed model. Time-to-event variables (e.g., time to death) will be analyzed using Cox proportional hazards model. Continuous variables (e.g. duration of hospitalization) will be analyzed using Mann Whitney test. Treatment effects on these variables will be estimated with 95% confidence intervals.

3. Safety Analyses

Serious adverse events will be summarized by grades and types using proportions and 95% confidence intervals for the two study arms. Relative safety profile of the two arms will be compared using Fisher's exact test.

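### The interim penalty halves a 0.05 alpha that the primary test does not have, so the go threshold after a formal interim analysis is undefined.

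*Combined protocol and SAP*

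**What the plan says.** Two sections of the combined protocol and SAP bear on this.

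**Statistical Analysis, item 1 (primary analysis, go/no-go decision, power).** The primary analysis is a one-sided Mann-Whitney test stratified by country. The go decision "will be a one-sided $P < .015$, suggesting evidence of promise of the treatment arm". The power statement uses another level: "a onesided Mann Whitney test at 15% level will have about 82% power to detect an odds ratio of 1.7". This item does not mention an interim penalty.

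**Halting Criteria for the Study, closing paragraphs on antibody-dependent enhancement.** "At any point should the DSMB require a formal interim analysis, we will examine the difference in treatment arms for need for mechanical ventilation". That comparison is adjusted for age and cardiopulmonary comorbidities. After the review and the DSMB's advice, "the IND sponsor will determine if study entry or study dosing should be interrupted". If the trial goes on, the final analysis is to account for the interim analyses held: "Therefore, we would penalize any final analysis dividing our 0.05 alpha in half for each interim analysis".

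The only 5% convention in the statistical section is the 95% confidence interval, used for secondary and ancillary effects ("Treatment effects on these variables will be estimated with 95% confidence intervals") and for safety ("Serious adverse events will be summarized by grades and types using proportions and 95% confidence intervals for the two study arms").

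**The concern.** A penalty for interim looks has to start from the level of the test that it penalises. This one starts from 0.05, which is neither the written go level nor the planning level of the primary test. It refers to any final analysis and does not exempt the primary one.

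The decision at stake is whether to go on to phase 3, possibly with these data carried into a seamless phase 2/3 analysis. If the DSMB asks for a formal interim and the trial continues, the team would have to settle the go threshold after a look at unblinded data. The text allows several answers, and they differ in direction as well as size.

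**Working it through.** **Inputs from the documents.** One-sided .015 (go rule); one-sided .15 with about 82% power, odds ratio 1.7, 146 vs 73 (power statement); 0.05 halved per interim (halting section); 20% mortality to Day 28 (secondary analyses). The pooled Day 28 distribution behind the 82% is not given, so it is assumed below and varied.

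**Step 1. Reproduce the 82%.** Under proportional odds,

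power = Φ( ln(OR)·√V − z(1−α) ), V = n1·n2·N / [3(N+1)²] · (1 − Σp³),

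where p are the pooled category proportions. With 146, 73 and N = 219, the first factor is 146·73·219 / (3·220²) = 16.075. For an assumed distribution of 50/15/2/3/3/7/20% over categories 1 to 7, Σp³ = 0.137, V = 13.88, and ln(1.7)·√V = 0.5306·3.725 = 1.977. Power at one-sided .15 is Φ(1.977 − 1.036) = 0.826. The plan's figure is reproduced at 15%.

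It cannot come from the other levels. With no ties at all (Σp³ = 0, a ceiling), ln(1.7)·√V = 2.128. Power is then at most Φ(2.128 − 1.645) = 0.685 at one-sided .05 and Φ(2.128 − 2.170) = 0.483 at .015.

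**Step 2. Apply the penalty as written.** The level after k looks is 0.05/2^k.

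| Reading of 0.05 | One look, one-sided | Against .015 | Against .15 |
|---|---|---|---|
| One-sided | .05/2 = .025 | .025/.015 = 1.67 times looser | .15/.025 = 6 times stricter |
| Two-sided | (.05/2)/2 = .0125 | .0125/.015 = 0.83, slightly stricter | .15/.0125 = 12 times stricter |

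On the one-sided reading a second look gives .0125, so the direction against .015 reverses between one look and two. Halving the primary levels themselves would give .0075 or .075; neither reading yields either figure after one look.

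**Step 3. Power at each level.** The noncentrality implied by the plan's own 82% at .15 is z(.85) + z(.82) = 1.0364 + 0.9154 = 1.9518. Power is Φ(1.9518 − z(1−α)).

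| One-sided level | z(1−α) | Power, calibrated to 82% | Range over assumed distributions |
|---|---|---|---|
| .15 | 1.036 | 82% | 75-86% |
| .075 | 1.440 | 70% | 61-76% |
| .025 | 1.960 | 50% | 40-57% |
| .015 | 2.170 | 41% | 32-49% |
| .0125 | 2.241 | 39% | 30-46% |

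The low end assumes 70/3/2/2/1/2/20% (Σp³ = 0.351, noncentrality 1.714). The high end is the no-ties ceiling, taken from the slightly larger form of V without the factor N/(N+1) (noncentrality 2.132). Simulations of the tie-corrected test, stratified and unstratified, fell within these ranges, as did unstratified runs with deaths set at 10% or 30%.

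**The case against.** The strongest reply is about scope. The sentence closes a safety-monitoring passage whose formal interim examines only need for mechanical ventilation. It may have been meant only for the final comparison of that variable, or only for the secondary and safety results reported with 95% intervals. On either reading the go rule is untouched. This is plausible, and the silence of the primary-analysis section supports it. But the sentence covers any final analysis and names no exception, so the scope is open.

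A second reply is that this only repeats the conflict between .015 and 15%. It does not: settling the primary level at either value leaves 0.05 matching neither.

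A third is that the penalty may never be used. It needs a formal interim and then continuation, and the documents give no likelihood for either. That limits the weight of the point. Even so, a formal question about an interim is built in once at least half of the participants have follow-up, and the DSMB may ask for one at any time.

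A reader might also infer that the penalty makes a go easier. That requires 0.05 to be one-sided, .015 to be the intended go level, and exactly one look. The documents do not state the sidedness, and the sentence is plainly meant to tighten the test. The risk that can be shown is an unclear threshold.

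**Conclusion.** The inconsistency stands and needs no assumption: the halting section penalises a 0.05 level that the primary test does not have, and leaves sidedness, scope and the maximum number of looks unstated. It should be corrected, but it matters only if a formal interim is held and the trial continues.

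The size depends on how the primary level is reconciled, and only one of these branches can apply:

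- If .015 is the go level, one look moves the threshold to .025 (power about 50% against 41% unpenalised) or to .0125 (about 39%).
- If 15% is the level, one look moves it to .025 or .0125, and power falls from 82% to about 50% or 39%. Halving .15 would leave about 70%.
- If the sentence covers only secondary, safety or ventilation analyses, the go rule does not change.

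A reader might quote the fall from 82% to 50% as the cost of the clause. The documents do not support this as a general statement, because it needs both the 15% level and a one-sided 0.05. The power figures rest on proportional odds and either the stated 82% or assumed pooled distributions. The levels are nominal levels for the final test and do not give the overall false-go rate. Confidence is high in the mismatch, and lower in the direction and size of its effect.

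**What to change.** First reconcile .015 and 15% in the primary-analysis section to one one-sided level; that is a separate point. Then replace the sentence that halves 0.05.

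**Preferred.** State that the formal look at need for mechanical ventilation is for safety only, cannot support an early efficacy claim, and leaves the final go threshold for the Day 28 outcome unchanged. This is coherent because the look does not test the Day 28 ordinal outcome. It costs one or two sentences and no power.

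**Alternative, if the sponsor keeps a penalty.** Apply it to the reconciled one-sided level, name the final analyses covered and the maximum number of looks, and report the resulting power for an odds ratio of 1.7. The wording is equally short, but the cost is power: for example, about 70% instead of 82% if .15 is halved once.

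The choice is a design decision for the sponsor and should be made before any formal interim.
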